Cover Page

APB Study: Apixaban Pharmacokinetics in Bariatric Patients

Objective: A study to determine the pharmacokinetics and pharmacodynamics of apixaban in obese patients who undergo bariatric surgery.

NCT02406885

IRB: IRB00035495 The Johns Hopkins University School of Medicine Note: Principal Investigator change/update – [name]

JHM IRB - eForm A – Protocol

- Use the section headings to write the JHM IRB eForm A, inserting the appropriate material in each. If a section is not applicable, leave heading in and insert N/A.
- When submitting JHM IRB eForm A (new or revised), enter the date submitted to the field at the top of JHM IRB eForm A.

APB Study: Apixaban Pharmacokinetics in Bariatric Patients

A study to determine the pharmacokinetics and pharmacodynamics of apixaban in obese patients who undergo bariatric surgery.

1. Abstract

a. Provide no more than a one page research abstract briefly stating the problem, the research hypothesis, and the importance of the research.

Obesity is now the leading health problem of the 21st century. Weight reduction by conservative methods including diet and exercise has had poor success rates. There has been a substantial increase in the use of bariatric surgery to provide sustained weight loss and thus a reduction in the medical comorbidities that are associated with obesity. However, because these procedures may alter the anatomical and physiological aspects of the gastrointestinal system, there is a possibility of altered pharmacokinetics to medications particularly when taken orally. Furthermore, patients typically lose anywhere from 50 to 75% of their estimated excess body mass approximately one to two years following surgery. This successful therapeutic outcome of the surgery may be causing long term changes in the pharmacokinetics that are independent of any direct anatomical or physiologic changes induced by the procedure.

Physicians and surgeons are very interested in oral anticoagulants for this special patient population. To date, there is no approved dosing for the obese patient (especially when considering surgical

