Hypothesis 2b: Patients who have recently undergone VSG surgery (1 month post-op) will have a decrease in both the Cmax and AUC, relative to pre-op values, when given a single dose of 5 mg of apixaban. The magnitude of the decrease in Cmax and AUC will be less than that seen in RYGB patients.

Rationale: Anatomic alteration of the GI tract will immediately reduce absorption in all postoperative bariatric patients. In RYGB patients, the attenuated small bowel and altered bile acid composition will lead to decreased absorption of the drug, whereas in sleeve gastrectomy patients prolonged gastric emptying may affect pharmacokinetics. These findings will be important when considering the use of apixaban as an oral anticoagulation option for perioperative VTE prophylaxis in the bariatric population, both in the acute hospital setting and after discharge in patients requiring extended VTE prophylaxis or treatment.

Hypothesis 2c: After undergoing bariatric surgery, patients at 6, and 12 months post-op will have an increase in Cmax and AUC, relative to pre-op values, when given a single dose of 5 mg of apixaban.

Hypothesis 2d: After undergoing RYGB, patients at 6, and 12 months post-op will have a greater increase in both Cmax and AUC, relative to pre-op values, than VSG patients relative to pre-op values when given a single dose of 5 mg of apixaban.

Rationale: Patients who are 6 to 12 months post-bariatric surgery generally have a 30-50% decrease in excess body weight. This decrease in body weight reduces volume of distribution of drug, potentially affecting Cmax. Results of the published Phase 1 apixaban study found that exposure to a dose of apixaban was inversely related to body weight. Therefore, we should expect higher plasma levels of apixaban in patients who are 6 to 18 months post-bariatric surgery when compared to pre-op values.

Findings of the Phase I study (3,4)

An open-label, parallel-group, non-randomized, single-dose study in healthy male and female subjects was conducted to assess the effects of body weight on the pharmacokinetics of a single 10 mg dose of apixaban. Following screening, patients were enrolled in one of three groups: low body weight (≤50kg, N=18), normal body weight (65-85kg, N=18) or high body weight (≥120kg, N=19).

Compared to normal body weight:

- There was a 27% increase in Cmax and 20% increase in AUC in patients with low body weight

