A recent review and meta-analysis of these new oral anticoagulants has concluded that they were equally as good as enoxaparin but did have a higher bleeding tendency. The drugs did not differ significantly for efficacy and safety. (24)

NOACs do not require routine coagulation monitoring and seem to be the way of the future for ease of administration efficacy and tolerability. Additional research is needed to determine how these new oral anticoagulants should be used in special populations such as the obese medical or surgical patient.

[figure not shown]

Figure 1 Mechanism of Action of Anticoagulants

*Derived from Dwek et al 2012

4. Study Procedures

a. Study design, including the sequence and timing of study procedures

Patients will be recruited from our preoperative bariatric surgical clinic (Roux-en Y gastric bypass, and vertical sleeve gastrectomy). Each patient will undergo a thorough history and physical exam (routine standard of care for bariatric patients) to document demographics including: age, sex, height, weight, body mass index and absence of the exclusion criteria. See Table 1 for sequence and timing of study procedures.

Table 1. Sequence and Timing of Study Procedures

Overview of Study Visits: Specific Aims 1, 2 and 3							
Study Visit Before and After Intervention		Specific Aim 1 Specific Aim 2		Specific Aim 3			
		Pharmacokinetics (Prior to Surgery)	Pharmacokinetics (Following Surgery)	Pharmacodynamics			
1	3 to 5 Weeks Prior to Bariatric Surgery (study participant receives one 5 mg dose of apixaban)	х		х			
2	1 Month (4 to 6 weeks) Post-bariatric surgery (study participant receives one 5 mg dose of apixaban)		x	x			
3	6 Months (6 to 8 months) Post-bariatric surgery (study participant receives one 5 mg dose of apixaban)		x	х			
4	12 Months (12 to 14 months) Post-bariatric surgery * (study participant receives one 5 mg dose of apixaban)		x	х			
5	Final Exit Interview Visit (two weeks following final visit)	Review any adverse events that may have occurred throughout entire study					

Note: Research participants in each group (RYGB, n=15; VSG, n=15; Total n=30) will undergo the study protocol detailed above.

*The patient ideally will have lost at least 30% to 50% of excess body weight by 12 months

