Study population: Obese patients with a body mass index (BMI) of 35 kg/m² or greater that have been approved for bariatric surgery at the Johns Hopkins Center for Bariatric Surgery from January 2015 until all patients recruited. (See Table 3. Timeline of Study)

Consenting subjects will be hospitalized overnight in the JHBMC Clinical Research Center. A single dose of 5 mg apixaban will be administered by experienced CRU nursing staff, and blood samples for apixaban concentration and factor Xa activity will be collected before administration of the apixaban dose and at 0.5, 1, 2, 3, 4, 6, 9, 12, 18, 24, 48 and 72 hours after dosing.

The participant will be hospitalized and monitored for a 24 hour duration and then released home when they meet discharge criteria. The participant will then be asked to return back to the CRU for one blood draw at 48 hours and one blood draw at 72 hours. At hours 48 and 72 hours we will have ±4 hour window to allow for travel and check in for the participant.

The apixaban concentrations will be measured at Pfizer (all specimens will be stored and batched for shipment to a commercial laboratory), and the factor Xa activity measured at JHH under the leadership and guidance of [name] Director of the Lab. (As per [name] expertise he has recommended the *chromogenic assay* that measures factor Xa activity using reagents from Siemens.)

Dose schedule, duration, and concurrent medications:

A single dose of 5 mg of apixaban will be given at approximately one month before bariatric surgery, then 1, 6 and 12 months followingbariatric surgery. Alterations in the pharmacokinetics of the bariatric surgical patient could be due to the anatomic changes in the gastrointestinal tract, the resulting weight loss or both. By examining patients who have had undergone the surgery but have not lost adequate weight loss, we can separate the effects of these two variables. There will be no required concurrent medications. Excluded medications are strong dual inhibitors and inducers of CYP3A4 and P-glycoprotein inhibitors and inducers (see Table 2). This table has been provided by [name] who is an anticoagulant expert and co-investigator of this study.

Table 2. Excluded medications

Drug Class	Examples	Impact of co- administration	Suggested Managment	

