To determine the durability or change in pharmacokinetics and pharmacodynamics of apixaban in patients with a body mass index (BMI) of 35 kg/m² or greater following one of two bariatric surgical procedures (pre-operative versus post-operative vertical sleeve gastrectomy or Roux-en-Y gastric bypass patients).

b. Secondary outcome variables.

1. To compare/contrast the pharmacokinetics and pharmacodynamics of apixaban in bariatric surgical patients who have undergone RYGB vs. VSG.

2. To determine how the pharmacokinetics of the drug may differ when there is significant post-operative surgical weight loss (>40% estimated excess body weight) 12 months following surgery versus those patients who have suboptimal weight loss following bariatric surgery (< 40% of estimated excess body weight).

c. Statistical plan including sample size justification and interim data analysis.

We propose to study 15 subjects in each arm (RYGB vs. VSG) and use them as their own controls. We have accounted for loss to follow-up (even with a 36% (5 in each group) drop-out rate, we would have enough subjects (10 per group) to demonstrate a 36 % change in AUC with an alpha error of 0.05 and a beta error of 0.2 (Power of 80%). If there is no loss to follow-up and all patients remain in the study, this will allow us to demonstrate a 29% change in AUC with an alpha error of 0.05 and a beta error of 0.2.

These calculations were calculated based on the following data from Upreti et al.: Ratio of geometric mean point estimated for high body weight (>120 kg) vs. normal body weight for C_{max} = 0.692 (0.586, 0.818) and AUC (INF) = 0.77 (0.652, 0.912).

Routine pharmacokinetic data will be determined, including C_{max}, T_{max} and AUC for each subject at each dosing time, and compared within subjects and between subjects and between groups. Factor Xa activity will be compared to apixaban concentration at each time point.

d. Early stopping rules.

While we do not expect to have any serious adverse events related to the administration of a single dose of 5 mg of apixaban as required in this study, we will interrupt the study and report to the IRB if 10% or more of our first 12 subjects suffer a serious adverse event "definitely

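### Secondary outcome 2 splits patients at 40% excess-weight loss with no planned group sizes: the lower group could be about 0 to 15 of 30, and a continuous analysis would use the data better

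*Combined protocol and SAP*

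**What the plan says.** Section 7b, item 2 sets one group with "significant post-operative surgical weight loss (>40% estimated excess body weight) 12 months following surgery versus those patients who have suboptimal weight loss". The second group is defined as "suboptimal weight loss following bariatric surgery (< 40% of estimated excess body weight". One side is strictly above 40% and the other strictly below, so a patient at exactly 40% is in neither.

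The protocol describes expected weight loss in three places:

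- Section 1 (Abstract): "patients typically lose anywhere from 50 to 75% of their estimated excess body mass approximately one to two years following surgery".
- Section 2, rationale to Hypotheses 2c and 2d: "Patients who are 6 to 12 months post-bariatric surgery generally have a 30-50% decrease in excess body weight".
- Section 4a, Table 1 footnote to the 12-month visit: "The patient ideally will have lost at least 30% to 50% of excess body weight by 12 months".

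Section 7c sizes the trial for the two surgical groups only, at 15 each, or 10 each after drop-out. For the weight-loss contrast it gives no expected numbers, precision or specific analysis. It says only, in general terms, that pharmacokinetic results will be compared within subjects, between subjects and between groups.

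**The concern.** The two groups are not set by design. They depend on how much weight patients happen to lose, so the information in the comparison depends on where 40% falls in that distribution. The protocol's three statements give different answers. Under the Abstract, 40% lies below the whole typical range and the lower group is a thin tail. Under the Section 2 rationale, 40% is the midpoint and the groups are about equal.

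If the lower group turns out to be one to three patients, those few determine the estimate and a null result says almost nothing. Whatever the group sizes, reducing a measured percentage to two categories discards information, which matters with only 20 to 30 patients.

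**Working it through.** **Inputs from the documents.** 30 patients (15 RYGB, 15 VSG). Section 7c allows for losing 5 per group, leaving 20; it labels this 36%, although 5/15 = 33%, so the counts are used here. The cut is 40%. The AUC ratio for high v normal body weight is 0.77 (0.652 to 0.912), with 19 and 18 subjects. **Not in the documents:** the SD and shape of weight loss, the level of that confidence interval, and the sidedness of alpha. Normal loss and two-sided 0.05 are assumed.

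**1. The plan's own figures.** With the interval read as 95%, log SD = [ln(0.912) − ln(0.652)] / (2 × 1.96) / √(1/18 + 1/19) = 0.0856 / 0.3289 = 0.260, so CV = √(exp(0.260²) − 1) = 0.265. A two-sample t-test on the percent scale at 80% power then needs 10 per group for a 36% change and 15 for 29%, as stated. If the interval is 90%, the log SD is about 0.305 to 0.310, and a log-scale decrease needs 9 and 14. The plan's sizing therefore reproduces, but it concerns groups of 10 or 15, not the weight-loss groups.

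**2. Expected size of the lower group.** Count = N × Φ((40 − mean)/SD).

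| Reading | Mean, SD | Share below 40% | Of 30 | Of 20 |
|---|---|---|---|---|
| 50-75% as central 80% | 62.5, 9.75 | 1.1% | 0.3 | 0.2 |
| 50-75% as mean ± 1 SD | 62.5, 12.5 | 3.6% | 1.1 | 0.7 |
| 50-75% as interquartile range | 62.5, 18.5 | 11% | 3.4 | 2.2 |
| Mean 50% | 50, 10 to 15 | 16-25% | 4.8-7.6 | 3.2-5.0 |
| 30-50%, symmetric | 40, any SD | 50% | 15 | 10 |

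In the second row, the chance of no such patient among 20 is (1 − 0.036)^20 = 0.48. The documents therefore allow about 0 to 15 of 30, or 0 to 10 of 20.

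**3. Precision by split, N = 30.** The standard error is proportional to √(1/k + 1/(30 − k)), which is 0.365 at k = 15.

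- 7 v 23: 0.432, or 1.18 times the even split.
- 5 v 25: 0.490, or 1.34 times.
- 3 v 27: 0.609, or 1.67 times.
- 1 v 29: 1.017, or 2.79 times.

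The SD of the contrast is not given. Borrowing a log SD of 0.254 to 0.305 from the cited interval, the decrease in AUC detectable at 80% power is 24-28% at 15 v 15, 27-32% at 7 v 23, 36-42% at 3 v 27 and 53-59% at 1 v 29. Power to detect a ratio of 0.77 is 62-78%, 48-63%, 28-37% and 13-16% respectively. With 20 completers, 10 v 10 detects 29-33% and 3 v 17 detects 38-43%.

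**4. Information kept by a cut.** For a linear relation and normal loss, information relative to the continuous variable is φ(z)² / [p(1 − p)], where p is the share below the cut.

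- Median split (p = 0.5): 0.159 / 0.25 = 0.64.
- Mean 50%, SD 10 to 15: 0.44 to 0.54.
- 50-75% as mean ± 1 SD: 0.18; as interquartile range: 0.37.

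Even the best-placed cut loses about 36%.

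**The case against.** A reader might infer that most patients will exceed 40%, that the lower group will be only about 1 to 7 of 30, and that the comparison therefore cannot be read. The documents do not support this. Only the Abstract clearly places typical loss above 40%, and 12 months is the earliest point of its window. The Section 2 range matches the 12-month visit more closely and centres on 40%. Taking 50% as its 12-month end assumes a time gradient that the text does not give. The Table 1 footnote states an ideal and does not put most patients above 40%. Unreadable is a fair description at one to three patients, but not at 7 v 23.

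A reader might also infer that the plan relies on this subgroup to separate anatomy from weight loss, since Section 4a says that by studying operated patients who "have not lost adequate weight loss, we can separate the effects of these two variables". That sentence follows the dosing schedule and reads at least as naturally as the 1-month visit, when anatomy has changed but weight has not. This fits the 1-month hypotheses (2a, 2b) set against the 6- and 12-month ones (2c, 2d), which also relate exposure to weight loss. Item 2 does not carry that question alone.

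Finally, this is an unpowered secondary outcome, and the plan names no test for it and does not rule out a continuous analysis. A single slope across both procedures could also mislead, because Section 2 notes that in RYGB greater weight loss and reduced absorption act in opposite directions. All of this stands: it lowers the severity and calls for a procedure term in the regression. It does not remove the information lost to the cut or the absence of planned group sizes.

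**Conclusion.** The point holds as a cheap improvement of low severity. The plan fixes a cut without saying how many patients it expects on each side, and its own weight-loss statements leave that number almost unconstrained. The consequence ranges from a modest loss of precision to a contrast too imprecise to interpret, and the documents cannot say which applies. The loss from dichotomising applies under every reading.

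The counts rest on assumed normal distributions and on how each quoted range is read. The information figures also assume a linear relation. The detectable differences borrow an SD from a different comparison and are indicative only.

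**What to change.** In Section 7b, item 2:

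- Make the analysis a regression of each patient's log(12-month / pre-op AUC), and likewise Cmax, on 12-month percent excess-weight loss as a continuous variable, with a term for procedure (RYGB v VSG).
- Report the fitted exposure ratio with its confidence interval at two or three stated amounts of weight loss.
- Keep the 40% split as a description only, and assign exactly 40% to one side.
- Reconcile the weight-loss figures in Section 1, the Section 2 rationale and the Table 1 footnote.

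The cost is plan wording. No new data are needed, because the split already requires each patient's 12-month percentage. The downsides are small: the regression assumes a roughly log-linear relation, which a plot of the 20 to 30 points can check, and the procedure term uses one degree of freedom. If the procedures differ greatly in weight loss, that term will widen the interval for the slope. The result remains an observational association, as the split would be.

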- There was a 31% decrease in Cmax and 23% decrease in AUC in patients with high body weight

The effect of RYGB vs. sleeve gastrectomy on long-term pharmacokinetics is difficult to predict because of the opposing effects of greater weight loss with reduced absorption in the RYGB patient.

These findings will be important when considering apixaban as an oral medication for long-term post-op bariatric patients who may require anticoagulation for stroke, myocardial infarction, atrial fibrillation or orthopedic procedures such as hip or knee replacements. (5, 6)

Specific Aim 3: To measure the effect of apixaban on Factor Xa activity (chromogenic anti-Xa activity assay) in bariatric surgical patients pre-operatively then at 1, 6, and 12 months post-operatively.

Hypothesis 3a: In spite of the changes in pharmacokinetics, the pharmacodynamics response (measured with a chromogenic anti-Xa activity assay) will not differ by more than 10% in comparing pre-surgical response to that at 1, 6, and 12 months after surgery.

Rationale: The changes in pharmacokinetics should not lead to a different concentrationresponse relationship in the chromogenic anti- Xa activity of individual patients following dosing with apixaban 5 mg. Were there to be a significant change in pharmacodynamics, other factors due to the altered anatomy or substantial weight loss would need to be invoked to explain that altered relationship.

3. Background (briefly describe pre-clinical and clinical data, current experience with procedures, drug or device, and any other relevant information to justify the research)

[figure not shown]
Defining Venous Thromboembolism

VTE includes both deep vein thrombosis (DVT), blood clots that form in the deep veins of the body, and pulmonary emboli (PE), blood clots that form in the deep veins of the body and then break free and enter the arteries of the lungs. VTE affects all races, ethnicities, both genders and all age groups. (1)

There is a fine balance between clot formation and fibrinolysis. Normally these two physiologic states are in dynamic equilibrium preventing patients from bleeding or clotting excessively. Numerous factors affect this delicate balance. These factors can be grouped into three broad categories, also known as Virchow's triad (after the German physician Rudolf Virchow):

- 1. Vascular injury (endothelial damage)
- 2. Activation of blood coagulation (hypercoagulability)
- 3. Venous stasis

Figure 1 Virchow's Triad

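### Secondary outcome 2 compares patients above and below 40% excess-weight loss with no procedure term stated, so a RYGB/VSG difference can be mixed with the weight effect

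*Combined protocol and SAP*

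**What the plan says.** Section 7b, secondary outcome 2, compares the pharmacokinetics at 12 months of patients who lost more than 40% of estimated excess weight with "those patients who have suboptimal weight loss following bariatric surgery (< 40% of estimated excess body weight"). The two surgical procedures are pooled in this contrast. RYGB versus VSG is a separate item, secondary outcome 1.

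The only analysis text is in Section 7c: Cmax, Tmax and AUC will be "compared within subjects and between subjects and between groups". No model, covariate or stratification is named for this or any other outcome.

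Three places in the protocol bear on whether procedure matters here:

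- Hypothesis 2d (Section 2) predicts that at 6 and 12 months RYGB patients "will have a greater increase in both Cmax and AUC, relative to pre-op values, than VSG patients relative to pre-op values".
- After the Phase I findings, Section 2 says that the long-term RYGB versus sleeve comparison "is difficult to predict because of the opposing effects of greater weight loss with reduced absorption in the RYGB patient".
- Section 4a, under the dose schedule, states the aim of separating anatomic change from weight loss by studying operated patients who have not lost enough weight.

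**The concern.** By the protocol's own account, procedure is linked both to the grouping variable (RYGB patients lose more weight) and to the outcome (RYGB reduces absorption). If RYGB patients make up more of the group above 40%, an unadjusted comparison of the two groups carries part of the procedure difference. A procedure effect could then be read as a weight effect, or could hide one. Using patients as their own controls does not remove this, because procedure can alter the change from pre-op itself.

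A second, separate cost is that a continuous measure is cut in two.

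One secondary contrast is at stake. The within-patient comparisons before and after surgery are not affected.

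**Working it through.** **The plan's own figure, used to fix the variability.** Section 7c cites "AUC (INF) = 0.77 (0.652, 0.912"), and Section 2 gives 18 normal-weight and 19 high-weight subjects. The interval level is not stated; I read it as 90%.

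- SE of the log ratio = ln(0.912/0.652)/(2 × 1.645) = 0.102.
- SD of log AUC = 0.102/√(1/18 + 1/19) = 0.310.
- SD of a paired difference = √2 × 0.310 = 0.439.
- A two-sided paired t-test with 80% power detects 0.996 SD at n = 10 and 0.778 SD at n = 15. The decreases are 1 − exp(−0.996 × 0.439) = 35.4% and 1 − exp(−0.778 × 0.439) = 28.9%.

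This matches the plan ("we would have enough subjects (10 per group) to demonstrate a 36 % change in AUC", and 29% with 15), so I use an SD of change of 0.44. As a second value I assume 0.31, which corresponds to a within-patient correlation of 0.5. The plan's power statement does not cover outcome 2.

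**Size of the mixing.** These are assumptions, not document figures: equal arms, normal weight loss with SD s centred on 40%, and RYGB d points above VSG. The RYGB share is Φ(d/2s) above 40% and 1 − Φ(d/2s) below. If R is the RYGB/VSG AUC ratio at equal weight, the >40%/<40% ratio is multiplied by R raised to the difference in shares.

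| d | R | s = 10: shares, factor | s = 18.5: shares, factor |
|---|---|---|---|
| 5 | 0.9 | 0.60/0.40, 0.98 | 0.55/0.45, 0.99 |
| 10 | 0.8 | 0.69/0.31, 0.92 | 0.61/0.39, 0.95 |
| 15 | 0.7 | 0.77/0.23, 0.82 | 0.66/0.34, 0.89 |

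The SD of 18.5 comes from the Abstract, which says "patients typically lose anywhere from 50 to 75% of their estimated excess body mass approximately one to two years following surgery": if 50 to 75% is the central half, SD = 12.5/0.6745 = 18.5. With d = 0 the shares are equal and the factor is 1. With d = 10, s = 10 and R = 1.1 or 1.2, the factor is 1.04 or 1.07.

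**Compared with the documented weight effect.** Section 2 reports: "There was a 31% decrease in Cmax and 23% decrease in AUC in patients with high body weight". On the log scale the s = 10 factors are 0.08, 0.33 and 0.75 of ln 0.77, so the illustrated mixing is smaller than that effect. To express the 23% on the scale of outcome 2, assume that it corresponds to 100% of excess weight and is log-linear. The slope is then −ln(0.77)/10 = 0.0261 per 10 points (+2.6%). The two groups differ by about 16 to 20 points in mean loss, so the expected weight effect across the split is +4 to +5%. Against that, the mixing is 0.5, 1.8 and 3.7 times as large, and the split would show +2%, −4% and −14%.

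**False rejection with no weight effect** (simulated, 20,000 trials per setting, s = 10, for the three rows of the table):

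- Split, 15 per arm: 5, 11 and 33% at SD of change 0.31; 5, 8 and 20% at 0.44.
- Split, 10 per arm, SD 0.44: 5, 7 and 15%.
- Regression on continuous loss plus procedure: about 5% throughout.

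**Cost of the cut.** Information kept = φ(z)²/[p(1 − p)], where p is the proportion below the cut. At p = 0.5 this is 0.1592/0.25 = 0.64, so 36% is lost. At p = 0.16 to 0.19 only 0.44 to 0.48 is kept. The number below 40% is not stated. Of 30 patients it would be 15 if loss centres on 40%, about 5 to 7 if on 50% (SD 10), and about 0 to 3 on the Abstract's range, which refers to one to two years.

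**The case against.** The strongest reply is that the protocol commits to no unadjusted test. No outcome has a model, Table 1 uses the word group for RYGB and VSG, and a comparison between groups could include procedure. That is fair, and it is why the point is that mixing can occur, not that it will. It does not settle the matter: neither that phrase nor the Section 4a aim balances procedure within the 40% split.

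Second, the downward cases conflict with Hypothesis 2d. Including weight at 2.6% per 10 points, their net RYGB/VSG change ratios are 0.91, 0.82 and 0.73, whereas 2d predicts a greater increase with RYGB. If 2d holds and absorption is still reduced, this slope limits the downward pull to about 0.3, 1 and 2%. This stands. The cases are illustrations that the protocol's admitted uncertainty about direction allows; they are not predictions.

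Third, significant versus suboptimal loss is a clinical grouping in a small study that claims no power for it, and regression would rarely reach significance. This also stands, and it is why the split is worth keeping as description.

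A reader might infer that the mixing outweighs the known effect of body weight. The documents do not support that. Against the reported 23% it is smaller in every case shown; the multiples of about half to over three arise only after the assumed rescaling to 4 to 5%.

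**Conclusion.** The point holds as a minor one. Outcome 2 is stated as a pooled split with no procedure term, and the protocol itself supplies the route by which procedure can enter the contrast. Neither size nor direction can be fixed from the documents, because they give neither the share above 40% by procedure nor the procedure effect at equal weight. The range runs from near zero (equal shares), through a downward pull of 1 to 18% in the illustrated cases, to an upward push of 4 to 7% if RYGB exposure at equal weight is higher. At the SD of change that matches the plan's own power figures, false rejection is near nominal in the low case and modestly raised in the middle one; only the extreme case is notable. The loss of at least 36% of the information rests on normality and linearity.

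It would go too far to conclude that outcome 2 will be biased, or biased downward.

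**What to change.** For outcome 2, state that the within-patient change from pre-op in log AUC and log Cmax at 12 months will be regressed on continuous percent excess-weight loss, with procedure as a covariate. Report the slope with its confidence interval, as an association. Keep the 40% comparison as a descriptive table by procedure, and state how many patients are expected below 40%. If the two-group contrast is to be tested, add procedure as a covariate; that removes the mixing in an additive model but not the information loss.

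The cost is analysis wording only, since outcome 2 already needs these data. The model assumes a roughly linear relation with a common slope in both procedures, and weight loss is not randomised. Intervals will be wide. The log half-width per 10 points at s = 10 is about t × SD/√(N − 2): for N = 30 and SD 0.31, 2.052 × 0.31/√28 = 0.120, or about ±13%. It is about ±17% with 20 patients, and ±19% and ±24% at SD 0.44. Power at the rescaled 2.6% slope is only about 6 to 7%. The gain is an estimate not mixed with procedure, rather than a significant test.
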